Program: /<folder>/<program_name>.sas

Page x of y

Programming note: Layout may change with the structure of the data.

L WHO

ACT-293987

Protocol: AC-065A309

Listing of WHO functional class

Analysis Set: Screened Analysis Set

Country: <country>, Site: <Site number>

Subject number	Visit	WHO functional class
1001003	Screening	II
	Visit 2 - Day 1	II*
	Visit 2 - Day 3	III
	Unscheduled	II
	Visit 3	I

* = Baseline

Output: <Output name>, Produced by DATAMAP on ddMMMyyyy hh:mm (CET),

SDTM Date: ddMMMyyyy

Program: /<folder>/<program_name>.sas

Page x of y

L_PK_CONC

ACT-293987

Protocol: AC-065A309

Listing of selexipag / ACT-333679 plasma concentrations

Analysis Set: Pharmacokinetic Analysis Set

Subject number	Visit	Timepoint	Selexipag concentration [ng/mL]	ACT-333679 concentration [ng/mL]
1001002	Visit 2 - Day 1	Pre-dose	xxx #	xxx #
		1 h post-dose	xxx	xxx
		2 h post-dose	xxx	xxx
		...		
	Visit 2 - Day 3	Pre-infusion start	xxx #	xxx #
		25 min post infusion start	xxx	xxx
		87 min post infusion start	xxx	xxx
		4 h post infusion start	xxx #	xxx #
		...		
1001003	...			

= Implausible plasma concentration

Output: <Output name>, Produced by DATAMAP on ddMMyyyy hh:mm (CET),

SDTM Date: ddMMyyyy

Program: /<folder>/<program_name>.sas

Page x of y

Programming note: List by subject. Only list subjects who provided data. Layout may change slightly depending upon data structure.

L_PK_DER

ACT-293987

Protocol: AC-065A309

Listing of derived PK parameters of selexipag and ACT-333679

Analysis Set: Pharmacokinetic Analysis Set

Parameter	Subject number	Time point	i.v. selexipag			Uptravi			Ratio i.v. selexipag / Uptravi	
			Dose [ug bid]	Selexipag	ACT-333679	Dose [ug bid]	Selexipag	ACT-333679	Selexipag	ACT-333679
Ctrough,ss [ng/mL]	1001002	Pre-dose	xxxx	xxx#	xxx#	xxx	xxx	xxx	xxx	xxx
	1001004	12 h post-dose	xxxx	xxx	xxx	xxx	xxx	xxx	xxx	xxx
Dose normalized Ctrough,ss,norm [ng/mL]	1001002	Pre-dose	xxxx	xxx	xxx	xxx	xxx	xxx	xxx	xxx
		12 h post-dose	xxxx	xxx	xxx	xxx	xxx	xxx	xxx	xxx
Cmax,ss [ng/mL]	1001002		xxxx	xxx	xxx	xxx	xxx	xxx	xxx	xxx
....										
Dose normalized Cmax,ss,norm [ng/mL]	1001002			xxx	xxx		xxx	xxx	xxx	xxx
....										
AUCtau,ss [ng*h/mL]	1001002		xxxx	xxx#	xxx#	xxxx	xxx	xxx	xxx	xxx
....										
Dose normalized AUCtau,ss, norm [ng*h/mL]	1001002			xxx	xxx		xxx	xxx	xxx	xxx
....										
tmax,ss [h]	1001002		xxxx	xxx	xxx	xxx	xxx	xxx		
....										

= Obtained from implausible plasma concentration
 Output: <Output name>, Produced by DATAMAP on ddMMMyyyy hh:mm (CET),
 SDTM Date: ddMMMyyyy
 Program: /<folder>/<program_name>.sas
 Page x of y

Programming note: List by parameter, then by subject. Do not display ratios for t_max.

L_PK_RATIO

ACT-293987

Protocol: AC-065A309

Listing of Cmax,ss and AUCtau,ss ratio of ACT-333679/selexipag

Analysis Set: Pharmacokinetic Analysis Set

Dose [ug bid]	Subject number	Cmax,ss Ratio		AUCtau,ss Ratio	
		Uptravi	i.v. selexipag	Uptravi	i.v. selexipag
200 ug b.i.d. p.o. / 225 ug b.i.d. i.v.	1001002	xxx	xxx	xxx#	xxx
	1001003	xxx	xxx	xxx	xxx
	1001005	xxx	xxx	xxx	xxx
400 ug b.i.d. p.o. / 450 ug b.i.d. i.v.	1001004	xxx	xxx	xxx	xxx
	1001010	xxx	xxx	xxx	xxx
...	1001006	xxx	xxx	xxx	xxx
Dose Normalized	1001002	xxx	xxx	xxx#	xxx
	1001003	xxx	xxx	xxx	xxx
	1001004	xxx	xxx	xxx	xxx
	1001005	xxx	xxx	xxx	xxx

= Obtained from at least one impalausible plasma concentration
 Output: <Output name>, Produced by DATAMAP on ddMMMyyyy hh:mm (CET),
 SDTM Date: ddMMMyyyy
 Program: /<folder>/<program_name>.sas
 Page x of y

Programming note: List by dose, then by subject. Only list subjects who provided steady state data.

L_IMP_CONC

ACT-293987

Protocol: AC-065A309

Listing of selexipag concentration in the infusion solution

Analysis Set: Pharmacokinetic Analysis Set

Subject number	Visit / Time point	Selexipag concentration (eCRF) [ug]	Actual selexipag concentration [ug]
1001002	Visit 2 - Day 2 IV-1	xxx	xxx
	Visit 2 - Day 2 IV-2	xxx	xxx
	Visit 2 - Day 3 IV-3	xxx	xxx
1001003	Visit 2 - Day 2 IV-1	xxx	xxx
	Visit 2 - Day 2 IV-2	xxx	xxx
	Visit 2 - Day 3 IV-3	xxx	xxx
1001006			

Actual selexipag concentration was assessed using a validated liquid chromatography with UV detector assay.

Output: <Output name>, Produced by DATAMAP on ddMMMyyyy hh:mm (CET),

SDTM Date: ddMMMyyyy

Program: /<folder>/<program_name>.sas

Page x of y

Programming note: List by subject. Only list subjects who provided data. Layout may change slightly depending upon data structure.

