2.3 Analysis periods

The study comprises five analysis periods:

Screening period: This period starts with the signing of the Informed Consent Form and ends with the first day of Period 1 (Visit 2 Day 1).

Period 1 (Uptravi, pre-treatment period, in-hospital): This period starts with intake of the morning dose of Uptravi at Visit 2 Day 1, and ends the following day before initiation of the first infusion of i.v. selexipag.

Period 2 (i.v. selexipag, treatment period, in-hospital): This period starts in the morning of Visit 2 on Day 2 with the start of the first infusion of i.v. selexipag, and ends after approximately 36 hours in the evening of Visit 2 on Day 3 with the resuming of administration of Uptravi at the evening dose.

Period 3 (Uptravi, post-treatment period): This period starts in the evening of Visit 2 Day 3 with the first dose of resumed oral administration of Uptravi, and ends 7 to 11 days later at Visit 3.

Safety follow-up period: This period starts at the end of Visit 3 and ends 30 to 37 days after the last administration of i.v. selexipag with the End-of-Study (EOS) telephone call (Visit 4).

[figure not shown]
A summary of analysis periods is presented in [Table 2](#):

Table 2 Summary of analysis periods

Period	Start	Stop
Screening period	Date/time of first Informed consent form signature	Prior to morning dose of Uptravi at Visit 2 Day 1
Period 1: Uptravi, pre-treatment period	Date/Time of Uptravi morning dose intake at Visit 2 Day 1	Prior to start of first infusion of i.v. selexipag at Visit 2 Day 2
Period 2: i.v. selexipag, treatment period	Start date/time of first infusion of i.v. selexipag at Visit 2 Day 2	Prior to evening dose of Uptravi at Visit 2 Day 3
Period 3: Uptravi, post-treatment period	Date/time of Uptravi evening dose intake at Visit 2 Day 3	Visit 3
Safety follow-up period	After end of Visit 3	End of Study

The study design and flow is shown in Figure 1 below. For details, refer to section 3 and section 7 of the AC-065A309 study protocol [D-17.055].

Figure 1 Study design and flow

* 12-hour PK profile after the morning dose.

** For convenience, hospitalization may be extended to the night before Day 1 and to the night of Day 3.

D = day; EOS = End-of-Study; IV1–IV3 = dose of i.v. selexipag; PK = pharmacokinetic; V = visit.

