7.6.1 Variables

The 12-lead ECG encompasses 3 categories of data obtained via the central ECG laboratory:

- Measurements:
 - ECG mean heart rate
 - PR interval,
 - QRS duration,
 - QT interval,
 - QTcB interval,
 - QTcF interval,
- Interpretation (normal/abnormal/unable to evaluate)
- Qualitative findings by category, as specified in the ECG data transfer specifications:

Table 11 Pre-specified ECG findings categories

Category
Atrioventricular Conduction
Axis and Voltage
Chamber Hypertrophy or Enlargement
Intraventricular-Intraatrial Conduction
Myocardial Infarction
Pacemaker
Sinus Node Rhythms and Arrhythmias
Supraventricular Arrhythmias
Supraventricular Tachyarrhythmias
ST Segment, T Wave and U wave
Ventricular Arrhythmias
Ventricular Tachyarrhythmias

ECG assessments will be performed at Visit 2 Day 1, Visit 2 Day 2 (pre-dose and 30 min after end of infusion for each of the two infusions), Visit 2 Day 3 (pre-dose and 30 min after end of infusion), Visit 3, and at unscheduled visits.

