7.6.3 Analysis

7.6.3.1 *Values over time*

A listing of all ECG measurements will be created displaying all values in the database. Abnormal ECG values will be flagged.

The overall interpretation and the findings will be presented in a separate listing.

For each parameter at each time over the course of the study, quantitative descriptive statistics for the value at the visit and the change from baseline will be presented by parameter and by time point.

Another descriptive summary will be provided for the absolute change from pre-dose to post-dose values in quantitative ECG parameters for the visits where pre- and post-dose values are assessed.

7.6.3.2 *Individual subject changes*

The number and percentage of subjects with at least one newly occurring or worsening abnormality for ECG parameters as defined in [Table 12](#) is provided by period as shown in [Table 7](#).

In addition, qualitative ECG findings will be tabulated by overall interpretation (normal, abnormal/unable to evaluate), and category [see [Table 11](#)].

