10.2.4 Unscheduled visits and visit windows

Assessments made on both, scheduled and unscheduled visits will be assigned to an analysis period according to [Table 2](#) using the assessment date and time.

Furthermore, each assessment will be assigned an analysis visit using the time windows described in [Table 13](#). If more than one assessment was made within a visit time window, the closest value to the target Visit is displayed in by visit displays.

Table 13 Analysis visit windows

Analysis visit	Nominal study day*	Lower bound study day*	Upper bound study day*
Visit 2, Day 1	Day 1	Day of informed consent	Day 1
Visit 2, Day 2	Day 2	Day 2	Day 2
Visit 2, Day 3	Day 3	Day 3	Day 3
Visit 3	Day 12	Day 4	Day 22
Visit 4	Day 33	Day 23	End of Study

* Study days are defined as in Section [10.2.2](#).

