...		xx	xxxx.x	xx.xx	xxxx.x	xxx	xxx	xx.xx	xxxx.x	xxx	xxx	xxxx.x	xx.xx	xxxx.x	xxx	xxx

pre = pre-dose assessment prior to infusion, post = post dose assessment (within 30 minutes after end of infusion)

SD = Standard deviation

Output: <Output name>, Produced by DATAMAP on ddMMMyyyy hh:mm (CET),

SDTM Date: ddMMMyyyy

Program: /<folder>/<program_name>.sas

Page x of y

Programming note: Continue for Total. Then repeat for PR Interval Single Beat [msec]; QRS Duration, Single Beat [msec]; QT Interval, Single Beat [msec]; QTcB Interval, Single Beat [msec]; QTcF Interval, Single Beat [msec].

T_EG_ABN

ACT-293987
Protocol: AC-065A309
Incidence of ECG abnormalities - QT prolongation, by period
Analysis Set: Safety Analysis Set

Period 2: i.v. selexipag treatment period

Parameter	Uptravi b.i.d. dose		
	200-1000 ug N=xxx n / m (%)	1200-1600 ug N=xxx n / m (%)	Total N=xxx n / m (%)
QTc (Bazett's correction), [msec]			
Value > 450 #	xxx / xxx (xx.x)	xxx / xxx (xx.x)	xxx / xxx (xx.x)
Value > 480 #	xxx / xxx (xx.x)	xxx / xxx (xx.x)	xxx / xxx (xx.x)
Value > 500 #	xxx / xxx (xx.x)	xxx / xxx (xx.x)	xxx / xxx (xx.x)
Increase from baseline > 30	xxx / xxx (xx.x)	xxx / xxx (xx.x)	xxx / xxx (xx.x)
Increase from baseline > 60	xxx / xxx (xx.x)	xxx / xxx (xx.x)	xxx / xxx (xx.x)
Value > 450 and increase from baseline > 30	xxx / xxx (xx.x)	xxx / xxx (xx.x)	xxx / xxx (xx.x)
Value > 450 and increase from baseline > 60	xxx / xxx (xx.x)	xxx / xxx (xx.x)	xxx / xxx (xx.x)
QTc (Fridericia's correction), [msec]			
Value > 450 #	xxx / xxx (xx.x)	xxx / xxx (xx.x)	xxx / xxx (xx.x)
Value > 480 #	xxx / xxx (xx.x)	xxx / xxx (xx.x)	xxx / xxx (xx.x)
Value > 500 #	xxx / xxx (xx.x)	xxx / xxx (xx.x)	xxx / xxx (xx.x)
Increase from baseline > 30	xxx / xxx (xx.x)	xxx / xxx (xx.x)	xxx / xxx (xx.x)
Increase from baseline > 60	xxx / xxx (xx.x)	xxx / xxx (xx.x)	xxx / xxx (xx.x)
Value > 450 and increase from baseline > 30	xxx / xxx (xx.x)	xxx / xxx (xx.x)	xxx / xxx (xx.x)
Value > 450 and increase from baseline > 60	xxx / xxx (xx.x)	xxx / xxx (xx.x)	xxx / xxx (xx.x)

n = Subjects with event, m = Subjects with QTc evaluation (at risk)

Baseline value below threshold OR baseline value above threshold and post baseline value worsened (increased)

If more than one ECG in a period has the same abnormality category, the subject is counted only once.

Output: <Output name>, Produced by DATAMAP on ddMMMyyyy hh:mm (CET),

SDTM Date: ddMMMyyyy

Program: /<folder>/<program_name>.sas

Page x of y

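### In the QT-prolongation table, the three absolute-threshold rows count any QTc increase in a subject already above the threshold, so they are inflated by noise, and more so in the i.v. period, which has the most ECGs

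*SAP*

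**What the plan says.** SAP 7.6.3.2 plans, by period, the number and percentage of "subjects with at least one newly occurring or worsening abnormality for ECG parameters" under the criteria of Table 12. It does not say what worsening means.

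The definition is in the # footnote of shell T_EG_ABN (SAP Appendix E): "Baseline value below threshold OR baseline value above threshold and post baseline value worsened (increased". The mark is on three of the seven rows for each QT correction: Value > 450, > 480 and > 500 ms. The other four rows require an increase of more than 30 or 60 ms, alone or combined with a value above 450. A further footnote says "If more than one ECG in a period has the same abnormality category, the subject is counted only once", so one qualifying ECG in the period is enough. The denominator m is every subject with a QTc evaluation, whatever the baseline.

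Baseline is the Day 1 assessment (SAP 10.2.3), when one ECG is scheduled. The later in-hospital ECGs are at "Visit 2 Day 2 (pre-dose and 30 min after end of infusion for each of the two infusions"), then before and after the single Day 3 infusion, followed by one at Visit 3 (SAP 7.6.1). On allocation, "Assessments made on both, scheduled and unscheduled visits will be assigned to an analysis period according to" Table 2 by date and time (SAP 10.2.4), and Period 2 begins at "Start date/time of first infusion of i.v. selexipag at Visit 2 Day 2" (SAP 2.3).

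**The concern.** For a subject already above a threshold, the rule compares the highest of the period's QTc readings with one baseline reading and accepts any excess. QTc varies from reading to reading, so some of these subjects will be counted with no drug effect at all. The chance rises with the number of ECGs, and the i.v. period has five times as many as either of the other two. A reader comparing the # rows across periods could see more QT prolongation on i.v. selexipag that comes only from the counting rule and the visit schedule. Protocol 6.2.3 lists ECG abnormalities as an endpoint for each period, and Protocol 1.3.1 says the study is to support regulatory filings.

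**Working it through.** **Figure in the plan.** None is stated for this rule, so there is nothing to reproduce.

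**ECGs per period (SAP 2.3, 7.6.1).** The IV-1 pre-dose ECG precedes the first infusion and falls in Period 1: k = 1. Period 2 holds IV-1 post, IV-2 pre and post, and IV-3 pre and post: k = 5. Period 3 with follow-up holds Visit 3 only, since Visit 4 is a telephone call: k = 1. Protocol 10.2.3.3 instead defines baseline as the latest ECG before study treatment, normally IV-1 pre-dose. Period 2 still has k = 5.

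**Without selection on baseline.** With exchangeable readings and no drug effect, the chance that at least one of k later values exceeds baseline is k/(k+1): 5/6 = 83% for k = 5 and 1/2 = 50% for k = 1. The rule, however, applies to subjects selected because baseline was high, so this is only an upper reference.

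**With selection.** Let baseline B = M + error and each later value = M + new error, with M normal (mean μ, SD σb) and errors normal (SD σw). With R = σb²/(σb² + σw²), M given B is normal with mean μ + R(B − μ) and variance Rσw². The share counted is

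p(k) = 1 − E[ Φ((B − M)/σw)^k | B > threshold ].

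The documents give no QTc mean or SD. Assumed: μ 420 or 435 ms, σb 15-25, σw 5-15. In the central case (435, 20, 10), R = 400/500 = 0.8, so a baseline of 465 implies an expected true level of 435 + 0.8 × 30 = 459 ms. That regression to the mean pulls the share below 5/6.

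| μ / σb / σw (ms) | Baseline > 450: Period 2 (k = 5) | One ECG (k = 1) |
|---|---|---|
| 420 / 15 / 15 (lowest) | about 44% | 15% |
| 420 / 20 / 10 | 62% | 28% |
| 435 / 20 / 10 (central) | 70% | 34% |
| 435 / 25 / 5 (highest) | 78% | 43% |

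In the central case the Period 2 share is 53% for the > 480 row and 40% for the > 500 row. If an increase > 30 ms were required, the Period 2 share at > 450 would be 0-10% (central 2%).

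**In subjects, at > 450 ms.** In the central case a baseline reading has SD √(20² + 10²) = 22.4, so P(B > 450) = P(Z > 15/22.4) = 0.25. Of 18 subjects, 18 × 0.25 = 4.5 start above 450. Chance cases among them are 4.5 × 0.70 = 3.2 in Period 2 and 4.5 × 0.34 = 1.5 in a one-ECG period. Over the assumed range the Period 2 number runs from 18 × 0.029 × 0.645 = 0.3 (420/15/5) to 18 × 0.303 × 0.693 = 3.8 (435/25/15).

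**Newly occurring cases.** In the central case, subjects with baseline at or below 450 cross it by chance in 27% (k = 5) against 11% (k = 1). So the worsening clause supplies 0.251 × 0.698 = 0.175 of a total 0.175 + 0.749 × 0.273 = 0.379, or 46%, of the chance cases in the Period 2 > 450 row. The rest come from unequal ECG counts alone.

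**The case against.** The strongest case against acting is that the table already contains the remedy. Four of seven rows per correction demand more than 30 or 60 ms, and a subject who moves from above 450 to above 480 is counted as new in the > 480 row. T_EG_SUM and T_EG_PREDS give changes at each time point without taking a maximum, L_EG lists every value, and with about 20 subjects each case can be inspected. The analysis is descriptive, QT is an other endpoint in SAP Table 7, and new-or-worsening counting is also used for laboratory values and blood pressure. An over-inclusive safety screen can be defended.

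Much of this stands, and it limits the consequence. It also rules out the reading that the whole by-period QT display is uninterpretable. It does not make the # rows comparable between periods, and the SAP is stricter in its own qualitative ECG table, where post-baseline rows show only findings absent at baseline.

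Two further points stand. The shares depend on the model: rounding QTc to whole milliseconds lowers them by up to about 3 points, and if half the within-subject variance were shared within a day, the central 70% would be about 65%. And the unequal ECG count also raises newly occurring cases, which redefining worsening cannot cure.

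**Conclusion.** The point holds for three rows under each of QTcB and QTcF. The any-increase rule creates cases without a drug effect, and at > 450 ms creates them in Period 2 at roughly 1.8 to 3 times the one-ECG rate under the assumed variability (central 70%/34% = 2.1). That excess in Period 2 follows from the text and the schedule; the percentages rest on an assumed normal model, because the documents give no QTc distribution.

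A reader might infer from 5/6 that about 83% of already prolonged subjects would be counted. The documents do not support that: these subjects are selected on a high baseline, every scenario gives less, and no single figure serves all three thresholds. The > 30 and > 60 ms rows do not use the any-increase rule. This is a cheap improvement to a descriptive safety table, not a threat to the study's conclusions.

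**What to change.** In SAP 7.6.3.2 and the T_EG_ABN footnote:

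- Limit both n and m of the three # rows to subjects whose baseline is at or below that row's threshold. This also settles a baseline exactly on the threshold, which the present footnote leaves out.
- Report subjects already above the threshold on a separate line with their own denominator, counting worsening only if the increase from baseline is > 30 ms, an existing Table 12 criterion.
- Add a footnote giving the scheduled ECGs per period (1, 5 and 1), because the unequal count still raises newly occurring cases in Period 2.

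The cost is a short addition to the SAP text, a revised footnote and one extra line per # row in the shell. No new data are needed. Small increases in subjects already prolonged leave the # rows but remain in the listing and the change-from-baseline summaries.

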1.2.4 Summary of clinical data

A comprehensive package of clinical studies was performed that supported the approval of selexipag as oral treatment for PAH. Details of the clinical development of selexipag oral formulation are described in the IB [\[Selexipag IB, Selexipag IB Amendment 1\]](#).

So far a different formulation of i.v. selexipag has been administered to 18 healthy male subjects in an absolute bioavailability study (AC-065-110) and has not been administered to subjects with PAH.

In the study AC-065-110, the geometric mean (95% confidence interval [CI]) of the area under the plasma concentration versus time curve (AUC) from 0 to infinity ($AUC_{0-\infty}$) of selexipag and ACT-333679 were 11.16 h·ng/mL (9.30, 13.38) and 14.91 h·ng/mL (11.42,

19.47), respectively, following a single i.v. infusion of 200 µg selexipag in healthy subjects. In the same study, following a single oral dose of 400 µg selexipag, geometric mean (95% CI) $AUC_{0-\infty}$ values of selexipag and ACT-333679 were 11.04 h·ng/mL (8.19, 14.87) and 37.97 h·ng/mL (30.18, 47.78), respectively. The exposure ($AUC_{0-\infty}$) to ACT-333679 was 1.34- and 3.44-fold higher than to selexipag after i.v. administration and oral administration, respectively. This difference in metabolite exposure is likely due to the first pass metabolism of oral selexipag [Selexipag IB, Selexipag IB Amendment 1].

Single doses of i.v. and oral selexipag were both well tolerated. The most frequently reported treatment-emergent adverse event (AE) was headache. All treatment-emergent AEs were of mild to moderate intensity. There were no serious adverse events (SAEs) and no AEs leading to discontinuation. No clinically significant treatment-emergent abnormality in clinical laboratory, vital signs, or ECG variables was observed.

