7.8.4.2 Trough concentrations

Selexipag and ACT-333679 $C_{\text{trough, ss}}$ will be listed by dose, subject, and period as well as the ratio of the periods per subject.

Summary statistics will be provided by dose, including dose normalized, and by period. Implausible $C_{\text{trough, ss}}$ values will be flagged in the listings and not included in summary statistics.

7.8.4.3 $C_{\text{max, ss}}$, $t_{\text{max, ss}}$, and $AUC_{\tau, ss}$

$C_{\text{max, ss}}$, $t_{\text{max, ss}}$, and $AUC_{\tau, ss}$ of selexipag and ACT-333679 will be listed by dose, subject, and period. The ratio of the parameters between i.v. selexipag (test treatment) and Uptravi (reference treatment) per subject will be shown, except for $t_{\text{max, ss}}$. Any values

obtained from implausible plasma concentrations of selexipag or ACT-333679 will be flagged in the listings and not included in the statistical analysis.

Summary statistics will be provided by dose and period for selexipag and ACT-333679.

Dose-normalized $C_{max, ss}$ and $AUC_{\tau, ss}$ will be listed and summarized by period as well for selexipag and ACT-333679.

$C_{max, ss}$ and $AUC_{\tau, ss}$ ratio of ACT-333679/selexipag will be listed by dose, subject, and treatment and will be summarized by dose and treatment.

The ratio of $C_{max, ss}$ and $AUC_{\tau, ss}$ of selexipag and ACT-333679 between Uptravi and i.v. selexipag, after dose normalization, within each dose level (if sufficient subjects are enrolled per level) will be estimated by fitting a mixed effect model to the data using period (i.e., treatment) as fixed, and subject as random effect to the log-transformed $C_{max, ss}$ and $AUC_{\tau, ss}$ values. The ratios of geometric means between i.v. selexipag (test treatment) and Uptravi (reference treatment) will be computed and displayed together with their 90% CI by back-transforming the period contrasts and interval boundaries of the log-transformed data. If dose-proportionality is shown within each dose, then an overall model may be considered for robustness.

The inter-subject coefficient of variation (CV_b) of $C_{max, ss}$ and $AUC_{\tau, ss}$ of selexipag and ACT-333679 will be computed by using the mean squared error (MSE) of the mixed model as an estimate of variation.

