Based on the previous studies QGUY/2006/NS304/-01, AC-065-101 and AC-065A201 it is known that the PK profile of selexipag and its active metabolite ACT-333679 is dose-proportional up to a single dose of 800 ug and for multiple doses of up to 1800 ug b.i.d. after oral administration.

Dose proportionality of $AUC_{\tau, ss}$ of selexipag and ACT-333679 after i.v. selexipag will be analyzed using the power model approach [Gough 1995], if at least three different dose levels with a sufficient number of subjects to compute CIs are included in the PKS. A plot of log dose versus log $AUC_{\tau, ss}$ including the slope of the estimated parameter will be displayed.

Differences in $t_{max, ss}$ of ACT-333679 between the i.v. selexipag period and the Uptravi period will be assessed within each dose level using a Wilcoxon signed rank test and displaying the median estimate and exact 90% CI of the location shift using Hodges-Lehmann estimation.

If considered appropriate, a sensitivity analysis may be conducted to evaluate the statistical impact of the plasma concentrations of selexipag or ACT-333679 that were considered implausible by the PK expert.

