This model equation can be fitted using a mixed linear model with $\log(D_i)$ as a covariate and subject as random effect. The 90% CI for the parameter estimate for the covariate will be computed. In case of dose proportionality, 1 should be included in the 90% CI of the parameter estimate.

SAS® code similar to the following will be used:

```
PROC MIXED data=<input_dataset>;  
  MODEL log_response=log_dose / DDFM=KR S CL ALPHA=0.1;  
  RANDOM intercept /subject=usubjid TYPE=UN;  
  RUN;
```

The assessment of dose proportionality using the power approach will only be conducted when at least three dose levels are included into the study.

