Ratio of geom. means (i.v./p.o)	xxx (xx.x, xx.x)	xxx (xx.x, xx.x)
90% CI	x.xxxx, x.xxxx	x.xxxx, x.xxxx
CV b[%]	xx.x	xx.x
CI = Confidence interval, n.e. = not estimable. p.o. = per os, b.i.d. = twice daily; i.v. = intravenous		
Geometric mean ratios were obtained by computing the anti-log of the treatment group difference of a mixed model with treatment as fixed and subject as random effect to the log-transformed data. CV_b[%] was computed using the mean squared error of residuals as a measure of variation. Values obtained from implausible plasma concentrations are not included in the analysis.		
Output: <Output name>, Produced by DATAMAP on ddMMMyyyy hh:mm (CET),		
SDTM Date: ddMMMyyyy		
Program: /<folder>/<program_name>.sas		
Page x of y		

Programming note: Display all dose levels. For dose levels not sufficiently populated to allow an estimation populate only 'n' row and show 'n.e.' for the remaining statistics.

T_PK_POW

ACT-293987

Protocol: AC-065A309

Dose proportionality of AUCtau of <selexipag/ACT-333679> after i.v. selexipag: Power model estimation

Analysis Set: Pharmacokinetic Analysis Set

n	beta	SE(beta)	90% CI
xxx	x.xxx	xx.xxxx	x.xxxx, x.xxx

CI = Confidence interval

Dose proportionality will be assumed if beta is close to 1, i.e., if the CI of beta includes 1.

Values obtained from implausible plasma concentrations are not included in the analysis.

Output: <Output name>, Produced by DATAMAP on ddMMMyyyy hh:mm (CET),

SDTM Date: ddMMMyyyy

Program: /<folder>/<program_name>.sas

Page x of y

Programming note: Produce table only if sufficient subjects are included in at least three dose levels.

T_PK_WIL

ACT-293987

Protocol: AC-065A309

Location shift analysis of tmax, ss of <selexipag/ACT-333679>

Analysis Set: Pharmacokinetic Analysis Set

n	i.v. selexipag - Uptravi Median	90% CI	p-value
xxx	x.xxx	x.xxxx, x.xxx	x.xxxx

CI = Confidence interval from a Hodges - Lehmann estimation.

p-value is derived from a Wilcoxon signed rank test.

Values obtained from implausible plasma concentrations are not included in the analysis.

Output: <Output name>, Produced by DATAMAP on ddMMMyyyy hh:mm (CET),

SDTM Date: ddMMMyyyy

Program: /<folder>/<program_name>.sas

Page x of y

[figure not shown]
F EXP

ACT-293987

Protocol: AC-065A309

Shift in selexipag dose between oral and i.v. treatment

Analysis Set: i.v. Safety Analysis Set

Output: <Output name>, Produced by DATAMAP on ddMMyyyy hh:mm (CET),

SDTM Date: ddMMyyyy

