Program: /<folder>/<program_name>.sas

Page x of y

Programming note: This is just a conceptual graphic showing subjects from two dose levels (there will be more levels in the study). Adapt to Actelion standards. Jitter series plots such that individual subject lines are clearly visible. Do use color for each series plot.

[figure not shown]
F PK POW

ACT-293987

Protocol: AC-065A309

Dose proportionality of AUC_{tau} <selexipag/ACT-333679> after i.v. selexipag: Power model estimation

Analysis Set: Pharmacokinetic Analysis Set

Values obtained from implausible plasma concentrations are not included in the analysis.

Output: <Output name>, Produced by DATAMAP on ddMMyyyy hh:mm (CET),

SDTM Date: ddMMyyyy

Program: /<folder>/<program_name>.sas

Page x of y

Programming note: This is just a general sketch: Display log dose vs. log AUC and display a regression line from the model with the slope of estimated beta. Add a second line with beta (i.e., slope) =1 as reference.

L_SCRF

ACT-293987

Protocol: AC-065A309

Listing of screening failures

Analysis Set: Screened Analysis Set

Country: <country>, Site: <Site number>

Subject number	Date	Reason for screening failure
1001001	ddMMyyyy	xxxxxxxxxxxxxxxxxxxxxxxxxxxxxxxxxxxx
1001002	ddMMyyyy	xxxxxxxxxxxxxxxxxxxxxxxxxxxxxxxxxxxx

Output: <Output name>, Produced by DATAMAP on ddMMyyyy hh:mm (CET),

SDTM Date: ddMMyyyy

Program: /<folder>/<program_name>.sas

Page x of y

Programming note: Add specification for reason of screening failure, if available from the database.

L_PWDS

ACT-293987

Protocol: AC-065A309

Listing of reasons for premature discontinuation from the study

Analysis Set: Screened Analysis Set

Country: <country>, Site: <Site number>

Subject number	Status	Date / Day	Reason for discontinuation from the study	Details
1001001	Completed	ddMMMyyy / xxx		
1001002	Discontinued	ddMMMyyy / xxx	Death	
1001003	Discontinued	ddMMMyyy / xxx	Physician decision	xxxx xxxxxxxxx

Output: <Output name>, Produced by DATAMAP on ddMMMyyyy hh:mm (CET),

SDTM Date: ddMMMyyy

Program: /<folder>/<program_name>.sas

Page x of y

L_PHYS

ACT-293987

Protocol: AC-065A309

Listing of physical examination results

Analysis Set: Screened Analysis Set

Country: <country>, Site: <Site number>

Subject number	Visit	Date / Day	Body system	Result	Specify abnormality	Clin. sign.
1001001	Screening	ddMMyyyy / xxx	General appearance Head, ears, eyes, nose, throat	Normal Abnormal	XXXXXXXXXX	No
	Visit 2 - Day 1	ddMMyyyy / xxx	...			

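### The T_PK_POW footnote treats a 90% CI for beta that includes 1 as grounds to assume i.v. dose proportionality, although this is only failure to reject

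*SAP*

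**What the plan says.** SAP 8.2.2.3 fits log AUC at steady state after i.v. dosing against log dose and reports the slope beta with a 90% CI. Its interpretive sentence is "In case of dose proportionality, 1 should be included in the 90% CI of the parameter estimate", which says what to expect if proportionality holds.

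The T_PK_POW shell in Appendix E prints n, beta, SE(beta) and the 90% CI. Its footnote adds the converse: "Dose proportionality will be assumed if beta is close to 1, i.e., if the CI of beta includes 1". Its programming note limits when the table appears: "Produce table only if sufficient subjects are included in at least three dose levels". The companion figure F_PK_POW has the instruction "Add a second line with beta (i.e., slope) =1 as reference". SAP 12.8 marks the table and the figure as key deliverables for both selexipag and ACT-333679.

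Protocol 10.3.5 describes the dose-proportionality analysis as exploratory, and SAP 8.2 says all tests and CIs are descriptive. The earlier evidence of proportionality cited in SAP 7.8.4.3 is "for multiple doses of up to 1800 ug b.i.d. after oral administration", so it does not cover the i.v. route.

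**The concern.** The two SAP statements run in opposite directions. The body text gives inclusion of 1 as a consequence of proportionality; the footnote makes it sufficient. The i.e. in the footnote also makes CI inclusion the whole definition of close to 1. Neither document gives a margin, a reference interval for beta or a maximum CI width.

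The rule is therefore a two-sided 10% test of beta = 1 with non-rejection read as a positive finding. If beta differs from 1, fewer evaluable subjects, a narrower dose range or noisier data all make the rule easier to satisfy. At stake is the accuracy of what a key table tells its reader about i.v. dosing, where the SAP cites no earlier evidence of proportionality.

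**Working it through.** The plan gives no precision, power or margin for beta, so there is no figure of its own to reproduce. The question is how often the rule would be met when beta is not 1.

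**Inputs**
- Between-subject SD of log AUC. Protocol 1.2.4 gives 95% CIs for geometric mean AUC after a single 200 µg i.v. infusion: 9.30 to 13.38 (selexipag) and 11.42 to 19.47 (ACT-333679). The 18 subjects were healthy men, and the protocol notes the formulation was not the one tested here: "So far a different formulation of i.v. selexipag has been administered to 18 healthy male subjects". Applying these SDs to steady-state AUC in PAH is an assumption.
- Sample size: 18, the target for the i.v. Safety Set (Protocol 10.5). The PK set could be smaller.
- Dose allocation (assumed, within the limits of 5–8 in Group A and 12–15 in Group B), in oral equivalents: one subject each at 200, 400, 600 and 800, two at 1000, and four each at 1200, 1400 and 1600 µg. The i.v. dose is 1.125 times the oral dose at every level, so spacing on the log scale is the same.
- True beta: illustrative. Nothing in the documents suggests a departure from 1.

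**Log-SD**

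SD = ln(upper/lower) / (2 × t(0.975, 17)) × √18, with t = 2.110.
- Selexipag: ln(13.38/9.30) = 0.3637; 0.3637/4.220 × 4.243 = 0.366.
- ACT-333679: ln(19.47/11.42) = 0.5335; 0.5335/4.220 × 4.243 = 0.536.

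**CI half-width**

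Each subject contributes one i.v. AUC, so the random intercept and residual act as a single variance and the fit is treated as ordinary regression with 16 df. For this allocation the sum of squares of log dose is Sxx = 5.18.
- SE = SD/√Sxx = 0.161 and 0.236.
- Half-width = t(0.95, 16) × SE = 1.746 × SE = 0.280 and 0.411.

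At these SDs an observed beta as low as 0.72 or 0.59 still meets the rule. Over the 8-fold range that is 1 − 8^(−0.280) = 44% or 1 − 8^(−0.411) = 57% lower dose-normalised AUC.

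**Probability that the 90% CI includes 1** (noncentral t, noncentrality (beta − 1)/SE)

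| True beta | Dose-normalised AUC over 8-fold | Selexipag | ACT-333679 |
|---|---|---|---|
| 1.0 | unchanged | 90% | 90% |
| 0.8 | 8^(−0.2) = 0.66, 34% lower | 67% | 79% |
| 0.7 | 8^(−0.3) = 0.54, 46% lower | 44% | 66% |

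**Sensitivity at true beta 0.7**
- Log-SD of 0.25, 0.30 or 0.65, same allocation: 17%, 30%, 73%.
- Three subjects at 200, three at 400 and twelve at 1600 µg: 12% and 40%.
- Base allocation with one of the two 1000 µg subjects moved to 200 µg: 29% and 56%.
- Group A entirely at 800–1000 µg: 80% and 85%. The range is then only 2-fold, where beta 0.7 means 1 − 2^(−0.3) = 19% lower, so this is a smaller departure than in the other rows.

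**The case against.** The strongest reply is that nothing turns on the footnote. T_PK_POW has no conclusion cell; it prints the estimate and CI, and the sentence is a fixed shell note that says assumed rather than shown. The body text states the correct direction, the figure carries a slope-1 line, and the three-level condition removes the sparsest cases. The rates above rest on borrowed SDs and an invented allocation, and moving one subject takes 44% to 29%.

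Most of this stands, and it keeps the point minor. The percentages say how often the condition would be met, not how often a table would carry a verdict. It does not rescue the sentence. A descriptive analysis needs no pass rule, the three-level condition sets no precision requirement, and this is the only place where the SAP says what inclusion of 1 is to be taken to mean.

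A reader might also infer that the footnote decides whether the i.v. and oral periods are compared in a pooled model, because SAP 7.8.4.3 says: "If dose-proportionality is shown within each dose, then an overall model may be considered for robustness". The documents do not support that. The sentence is permissive, speaks of proportionality within each dose, and does not refer to T_PK_POW; the T_PK_MM shell already contains a dose-normalised row without any condition. Nor should one go the other way and say that the pooled i.v./oral ratio is free of any proportionality assumption because the dose correspondence is a constant 1.125. That holds for planned doses, but SAP 7.8.3.1 normalises by the actual dose.

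**Conclusion.** Wrong as written, minor. The logical fault depends on none of the assumed numbers: inclusion of 1 in a 90% CI is non-rejection, and the footnote reads it as grounds for assuming proportionality. Its size does depend on them. Under the base assumptions a slope of 0.7 satisfies the rule in roughly 44% (selexipag) and 66% (ACT-333679) of trials, and the figure runs from 12% to 85% over the allocations tried.

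The consequence is confined to a wrong reading in the report. Proportionality is not a study objective and no stated decision uses it. The calculation shows that the interval is likely to be wide; it is not evidence that i.v. exposure departs from proportionality.

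**What to change.** Delete the footnote sentence in T_PK_POW, or replace it with: beta and its 90% CI are descriptive; inclusion of 1 does not establish dose proportionality. The wording in SAP 8.2.2.3 can stay.

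Optionally, add one line to the table giving (highest dose/lowest dose)^(beta − 1) with its 90% CI, so that the reader sees the implied change in dose-normalised AUC over the doses studied. It should carry a note that the slope is between-subject, because each subject receives a single i.v. dose level that follows from earlier individual titration.

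The cost is one sentence of SAP text and, if wanted, one derived line in the shell. No new data or model is needed. The table would no longer support a statement that proportionality is assumed. No change to SAP 7.8.4.3 or T_PK_MM is needed for this point.
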